6.2 Justification for Study Design, Dose, and Endpoints

The study is double-blind and placebo-controlled to avoid subjective bias in the assessment of the safety and tolerability of CVN766. Dose escalation will be predicated on a review of available blinded safety, tolerability, and PK data observations for each prior dose cohort.

The sponsor has selected the starting dose level considering the FDA Guidance for Industry (Estimating the Maximum Safe Starting Dose in Initial Clinical Trials for Therapeutics in Adult Healthy Volunteers, 06 July 2005) and providing additional safety factors to the initial calculations based on the principles outlined in the guidance. The toxicity profile of CVN766 after oral dosing was examined in repeat dosing studies in rats and dogs. Scaling based on body surface area was conducted by multiplying the NOAELs for the most sensitive animal species by the appropriate conversion factors. Based on these calculations and applying a 10-fold safety margin below the NOAEL human-equivalent dose (HED), the maximum recommended starting dose (MRSD) for this first-in-human study is 167 mg for a 60 kg subject. The selected starting dose level is 5 mg.

The study's multiple-ascending dose (MAD) portion seeks to prepare for subsequent repeat dosing studies in subjects. Each MAD dose level will have been studied or exceeded in the SAD portion of the study before its use in a MAD cohort.

Nonclinical toxicity study data provide a basis for calculating the maximum exposure level that can be presumed safe. Escalating to the HED of the NOAEL in the most sensitive animal species, the maximum dose for clinical use is 1670 mg/day.

The projected $t_{1/2z}$ in animal species ranged up to 6.5 hours, so sample collection through Inpatient Discharge 72 hours post-dose is expected to correspond to more than 5 half-lives and is anticipated to be adequate to document elimination of CVN766. The study design allows for collecting additional PK samples at later timepoints if preliminary emerging PK results are indicated.

AEs, physical exams, vital signs, ECG findings, and clinical laboratory results are used as safety assessments to determine dose tolerability and dose-limiting effects of CVN766. The plasma PK and CSF parameters and PK endpoints will help elucidate the pharmacology of CVN766.

Samples for DNA analysis will be collected and may be used to evaluate drug metabolic enzyme and transporter polymorphisms that may contribute to the variability in the PK of CVN766.

6.3 Premature Termination or Suspension of Study or Investigational Site

6.3.1 Criteria for Premature Termination or Suspension of the Study

The study will be completed as planned unless new information or other evaluation regarding the safety of the study medication indicates an adverse change in the risk profile for the compound, such that the SRG or Institutional Review Board (IRB) considers the risk is no longer acceptable for subjects participating in the study.

In addition, if any of the following occur, further dosing will be withheld until the SRG reviews the relevant data, including unblinded data (if deemed necessary by the SRG request), and will decide whether it is safe to suspend dosing or continue dosing at either the planned or alternative dose levels or decides to prematurely terminate the study:

1. Two or more subjects in any single cohort or across more than 1 cohort experience the same type of serious or Medically Significant event as defined by the Investigator
2. Two or more subjects in any single cohort or across more than 1 cohort experience alanine aminotransferase (ALT) and/or aspartate aminotransferase (AST) elevations $>5 \times$ upper limits of normal (ULN) in the absence of a concomitant bilirubin increase (see point 3 below)
3. One or more subjects in any single cohort or across more than 1 cohort experience ALT and/or AST elevations $>3 \times$ ULN in the presence of a total bilirubin increase $>2 \times$ ULN or an international normalized ratio (INR) >1.5 without findings of cholestasis or other alternate etiology to explain the elevations (i.e., “Hy’s Law cases”)
4. Two or more subjects in any single cohort or across more than 1 cohort experience ALT and/or AST elevations $>3 \times$ ULN with the appearance of fatigue, nausea, vomiting, right upper quadrant pain or tenderness, fever, rash, and/or eosinophilia ($>5\%$).

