6.1.2 Part 2: Multiple-Dose Regimen

For the multiple-dose regimen, approximately 24 subjects will be enrolled in 1 of the 3 multiple-dose cohorts (designated as M1 through M3, respectively) in an ascending fashion. Dosing will be administered in the fasting state; this can be changed by the SRG if exposure is found to be higher in the fed state. The dose levels planned to be studied in the multiple-dose regimen (M1 through M3) are provided in Table 5. Each multiple-dose cohort will consist of 8 subjects randomized to CVN766 or placebo, whereby 6 subjects will receive a daily dose of CVN766, and 2 subjects will receive matching placebo for 7 days. However, the duration may be increased to ≤14 days at the discretion of the safety review group (SRG) if preliminary PK data suggest steady-state will not be achieved within 6 days of daily dosing. Unlike the single-dose regimen, sentinel dosing within cohorts is not required in the multiple-dose regimen.

Subjects for all multiple-dose cohorts will be admitted to the study unit 1 day prior to dosing and remain in the unit for the duration of the dosing period and for at least 48 hours after the last dose for safety and PK assessments before discharge. On treatment Days 1 and 7, subjects will undergo safety monitoring and PK sampling from blood plasma through 48 hours post-dose and, in cohort M1 only, from urine through 24 hours post-dose. In cohorts M1 and M2, on treatment Day 7 (or last day of dosing, if extended beyond Day 7), subjects will additionally undergo PK sampling from CSF via lumbar puncture at 3 hours post-dose. If needed to resolve questions arising from prior cohorts' data, subjects in cohort M3 also may, at SRG discretion, undergo PK sampling from CSF via lumbar puncture, the choice of day (e.g., Day 1 or Day 7) and sampling time to be decided by SRG. Subjects in MAD cohorts may be asked to return to the clinic for an additional plasma PK sample 3 days after the last dose (e.g., Day 10) depending on emerging PK data, i.e., $t_{1/2}$. The total confinement period will be 9 nights unless extended for additional dosing days or for management of AEs. Follow-up assessments will occur approximately 7 and 14 days after the final dose. A summary of multiple-dose study visits is included in Appendix A.

Table 2 Multiple Dose Visit Schedule

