6.1.3 Dose Escalation

The SRG will be comprised of the Investigator, Medical Monitor, Cerevance Responsible Medical Officer and may include other Cerevance representatives. A pharmacokineticist and other subject matter experts may participate as needed. The SRG will be responsible for ongoing review of safety, tolerability, clinical laboratory results, and available PK data and deciding to:

- Expand each single-dose cohort from the sentinel cohort to the full cohort (based on a review of at least 24 hours post-dose safety data from each of the sentinel subjects),
- Escalate to the next planned cohort or alternative dose levels (e.g., lower, intermediate, or higher) in single-dose cohorts (based on a review of available data including at least 72 hours post-dose safety data and clinical laboratory results from each of the subjects in the current cohort),
- Escalate to the next planned cohort or alternative dose levels (e.g., lower, intermediate, or higher) in multiple-dose cohorts (based on a review of available data including at least 48 hours post 7th dose safety data from each of the subjects in the current cohort),
- Add additional dose cohort(s) in either the single- or multiple-dose studies,
- Increase the duration of dosing in the multiple-dose cohorts from 7 days to ≤ 14 days

If 2 or more subjects in a single cohort experience the same type of serious or medically adverse event, further dosing will be withheld until the SRG investigates the events. Based on this assessment, the SRG will determine if the study should be terminated or continued and whether modification of planned dose levels and/or implementation of additional safety monitoring is indicated.

For each cohort (including sentinel subjects, where applicable), the SRG will carefully review the available blinded safety, tolerability, clinical laboratory results, and PK data to determine whether dosing should stop or continue (and, if continued, at what dose, including whether to repeat the previous dose), whether additional sequential dosing should be implemented in future cohorts or whether the blind should be broken to identify whether the subjects received CVN766 or placebo. However, precautions must be taken not to unblind the study staff, including the investigator.

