7.5 Criteria for Discontinuation or Withdrawal of a Subject

The primary reason for discontinuation or withdrawal of the subject from the study or study medication should be recorded in the eCRF using the following categories. For screen failure subjects, [Section 9.1.15](#).

1. The subject has experienced a PTE or AE that requires early termination because continued participation imposes an unacceptable risk to the subject's health or the subject is unwilling to continue because of the PTE or AE.
2. Liver Function Test (LFT) Abnormalities
Study medication should be discontinued immediately with appropriate clinical follow-up (including repeat laboratory tests, until a subject's laboratory profile has returned to normal/baseline status) if the following circumstances occur at any time during study medication treatment:
 - ALT or AST $>8 \times$ ULN, or
 - ALT or AST $>5 \times$ ULN and persists for more than 2 weeks, or
 - ALT or AST $>3 \times$ ULN in conjunction with elevated total bilirubin $>2 \times$ ULN or INR >1.5 , or
 - ALT or AST $>3 \times$ ULN with the appearance of fatigue, nausea, vomiting, right upper quadrant pain or tenderness, fever, rash and/or eosinophilia ($>5\%$).
3. Significant protocol deviation. The discovery post-randomization that the subject failed to meet protocol entry criteria or did not adhere to protocol requirements and continued participation poses an unacceptable risk to the subject's health.
4. Lost to follow-up. The subject did not return to the clinic and attempts to contact the subject were unsuccessful. Attempts to reach the subject must be documented.

5. Voluntary withdrawal. The subject (or subject's legally acceptable representative) wishes to withdraw from the study. The reason for withdrawal, if provided, should be recorded in the eCRF.

Note: All attempts should be made to determine the underlying reason for the withdrawal, and, where possible, the primary underlying reason should be recorded (i.e., withdrawal due to an AE).

6. The sponsor, IRB, IEC, or regulatory agency terminates the study.
7. Other.

Note: The specific reasons should be recorded in the "specify" field of the eCRF.

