9.7.6 Causality of AEs

The relationship of each AE to study medication(s) will be assessed using the following categories:

- Related: An AE that follows a reasonable temporal sequence from the administration of a drug (including the course after withdrawal of the drug), or for which possible involvement of the drug can be argued, although factors other than the drug, such as underlying diseases, complications, concomitant drugs, and concurrent treatments, may also be responsible.
- Not Related: An AE that does not follow a reasonable temporal sequence from the administration of a drug and/or that can reasonably be explained by other factors, such as underlying diseases, complications, concomitant drugs, and concurrent treatments.

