9.8.2 Collection and Reporting of SAEs

When an SAE occurs through the AE collection period it should be reported according to the following procedure:

An SAE form must be completed in English and signed by the investigator immediately or within 24 hours of the first onset or notification of the event. The information should be completed as fully as possible but contain, at a minimum:

- A short description of the event and the reason why the event is categorized as serious
- Subject identification number
- Investigator's name
- Name of the study medication(s)
- Causality assessment

The SAE form should be transmitted within 24 hours to the attention of the contact listed in Section 1.0.

Any SAE spontaneously reported to the investigator following the AE collection period should be reported to the sponsor if considered related to study participation.

Reporting of Serious PTEs will follow the procedure described for SAEs.

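### Section 6.3.1 requires a dosing hold after one subject only for a Hy's Law case; a single drug-related serious event of any other kind requires none, which matters mainly during daily multiple dosing

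*Protocol*

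**What the plan says.** Section 6.3.1 has four criteria. If any is met, dosing stops until the SRG has reviewed the data, unblinded if it asks. Item 1 is "Two or more subjects in any single cohort or across more than 1 cohort experience the same type of serious or Medically Significant event". Items 2 and 4 are liver criteria that also need two subjects. Item 3, the Hy's Law criterion, is the only one that starts from a single subject: "One or more subjects in any single cohort or across more than 1 cohort experience ALT and/or AST elevations".

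The multiple-dose (MAD) part has no required sentinels (Section 6.1.2): "Unlike the single-dose regimen, sentinel dosing within cohorts is not required in the multiple-dose regimen". Dosing is daily for 7 days and may be extended to at most 14. Escalation to the next MAD cohort needs a "review of available data including at least 48 hours post 7th dose safety data from each of the subjects" in the current cohort (Section 6.1.3).

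The plan also contains these safeguards:
- Section 6.1.3 makes the SRG responsible for continuing safety review, and requires it to look at each cohort's blinded data and decide whether dosing stops or goes on. It also has all treatment-period adverse events evaluated against the criteria of 6.3.1.
- Section 7.5 stops the individual: "The subject has experienced a PTE or AE that requires early termination because continued participation imposes an unacceptable risk".
- Section 9.8.2 sets a reporting deadline: "An SAE form must be completed in English and signed by the investigator immediately or within 24 hours".
- Section 6.2 promises prior single-dose (SAD) coverage: "Each MAD dose level will have been studied or exceeded in the SAD portion of the study before its use in a MAD cohort".

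**The concern.** This is a first-in-human study. A single related death, convulsive seizure or anaphylactic shock would not meet item 1. Nor would two serious events of different types in two subjects. The sponsor already accepts that one subject is enough for a Hy's Law liver signal, so the higher threshold for every other serious event is hard to justify.

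The gap matters most in the MAD part, where the remaining subjects are due another dose within a day. Whether a first related serious event pauses their dosing is better settled beforehand than decided between two doses.

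**Working it through.** The plan gives no operating characteristic for these rules, so there is no figure to reproduce. The check has two parts: whether any clause supplies the missing hold, and what the schedule implies if none does.

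**1. Required holds in 6.3.1**

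| Item | Event | Subjects needed |
|---|---|---|
| 1 | Serious or Medically Significant, same type | 2 or more |
| 2 | ALT/AST above 5 × ULN, no bilirubin rise | 2 or more |
| 3 | Hy's Law: ALT/AST above 3 × ULN with bilirubin above 2 × ULN or INR above 1.5, unexplained | 1 or more |
| 4 | ALT/AST above 3 × ULN with symptoms | 2 or more |

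Item 1 counts within and across cohorts and does not depend on causality. The Study Summary and 6.1.3 repeat a two-subject, same-type rule.

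**2. Could another clause supply the hold?**

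| Clause | What it requires | Holds other subjects after one event? |
|---|---|---|
| 6.3.1, opening risk clause | SRG or IRB judgement | No trigger |
| 6.1.3, SRG review of each cohort | Review, then a decision on dosing | Required, but not tied to one event or timed before the next dose |
| 6.1.3, adverse event evaluation | Assessment against 6.3.1 | Returns to the table above |
| 6.1.3, MAD escalation review | Data to 48 h after dose 7 | Gates the next cohort |
| 7.5 | Stops the affected subject | No |
| 8.5 | Escalation may be interrupted | Permissive, and about escalation |
| 9.8.2 | Report within 24 h | Reporting only |

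None does.

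**3. Timing.** The 7th dose is on Day 7. Adding 48 h gives Day 9 as the earliest escalation review, after a 7-day cohort has finished dosing. If dosing were extended, that condition could be met while doses continue, but it still governs escalation and not continued dosing.

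**4. Scheduled doses left.** Inputs are 6 active subjects per MAD cohort and 7 or 14 daily doses (6.1.2). I assume the affected active subject stops after the Day d dose, leaving 5.
- 7 days: 5 × (7 − d) = 30, 25, 20, 15, 10, 5 for d = 1 to 6.
- 14 days: 5 × (14 − d) = 65 for d = 1, 60 for d = 2, down to 5 for d = 13.

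**5. How often the first event stands alone.** The plan gives no event rate. Assume 1% to 5% per active subject, independent, n = 6:
- At least one: 1 − 0.99⁶ = 0.059; 1 − 0.95⁶ = 0.265.
- Exactly one: 6 × 0.01 × 0.99⁵ = 0.057; 6 × 0.05 × 0.95⁵ = 0.232.
- Two or more: 0.059 − 0.057 ≈ 0.0015 before rounding; 0.265 − 0.232 = 0.033.

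At such rates a cohort with any event nearly always has just one. The two-or-more figures also treat every event as the same type, so they flatter the present rule within a cohort. They leave out a matching event in another cohort, which item 1 would count.

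**The case against.** The strongest reply is that review is a duty. The SRG must review safety on a continuing basis and must decide, cohort by cohort, whether dosing goes on. The setting helps too: there is one site, MAD subjects are inpatients throughout dosing, every dose is given under the Investigator's supervision, and the Investigator and Medical Monitor both sit on the SRG. A reader might infer from 6.3.1 that dosing would simply carry on after a related death, or that nobody is obliged to look. The documents do not support that. What they lack is narrower: a trigger, a deadline before the next dose, and an automatic pause.

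The dose margins also count. M1 (45 mg) and M2 (125 mg) lie below the 167 mg maximum recommended starting dose, which already includes a 10-fold margin. M3 (250 mg) is 1670 / 250 ≈ 6.7-fold below the human-equivalent NOAEL dose. Repeat dosing was studied in rats and dogs, and each MAD dose is matched or exceeded in SAD first. This makes an event less likely. It does not say what happens to the other subjects after one, and SAD experience does not cover repeat dosing in humans.

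Third, the two-subject threshold is used consistently and is a design choice; nothing in the protocol demands a one-event rule. That is fair, and it is why this is a cheap improvement and not an error in the plan.

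Finally, 25 doses might be read as expected exposure. It is not: it supposes that the event occurs and that nobody acts.

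**Conclusion.** The point holds as a should-fix. The textual reading is firm: outside Hy's Law, no clause requires other subjects' doses to be withheld after one drug-related serious event. SRG review is required, but it is neither event-triggered nor timed to the next daily dose. The gap is widest in MAD. It is smaller in SAD, which has one dose per period, a sentinel pair with a 24 h review, and SRG review before each escalation. It is not absent there: the S3 fed period has no sentinels, and the later S3 fasted subjects may be dosed at two-day intervals.

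The practical size is uncertain because it depends on an event rate the plan does not give and on how quickly the SRG would act. The remaining-dose counts are a schedule upper bound, given for context only; they do not measure risk.

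**What to change.** Add a criterion to 6.3.1: one subject with a serious event assessed as Related to study drug (9.7.6) withholds further dosing until SRG review, unblinded if needed. Keep item 1 for serious events regardless of causality. As a tidy-up, align 6.1.3 and the Study Summary with 6.3.1 on counting across cohorts and on the term Medically Significant event; 6.3.1 already applies through the cross-reference in 6.1.3, so this is secondary.

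The amendment is short. The SRG exists, and seriousness and causality are already recorded for each event. It is a pause, and dosing may resume after review.

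The downside is an occasional unscheduled review or pause that may disturb one MAD cohort's steady-state PK. Related is broad in 9.7.6, since it takes in an event "for which possible involvement of the drug can be argued", so the trigger is wider than item 3 and could fire for an event also attributed to lumbar puncture. If 1% to 5% of subjects had a serious event marked Related (assumed; all subjects counted because causality is judged blinded), the extra reviews would number 24 × 0.01 = 0.24 to 24 × 0.05 = 1.2 in MAD, and 64 × 0.01 = 0.64 to 64 × 0.05 = 3.2 in the whole study.

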If all doses are tolerated, then additional cohorts with higher doses may be considered; The actual choice of the subsequent dose level will occur after the full review of the available blinded safety, tolerability, clinical laboratory results, and available PK data in the preceding cohort. The subsequent dose level may be higher, lower, or remain the same as the preceding dose level. If necessary, additional cohort(s) may be added to fully characterize the safety and tolerability of CVN766.

Initiation of the multiple-dose regimen will only occur after a full blinded review of all available safety, tolerability, and clinical laboratory results for the fasting drug administration to single-dose Cohort S3 (minimally including samples collected through Day 4) and available PK data. For each multiple-dose cohort after the first, the actual choice of dose level may be modified by the SRG after review of the available blinded safety, tolerability, and clinical laboratory results and PK data in the preceding multiple-dose and next-higher-dosage single-dose cohorts (i.e., multiple-dose Cohort M2 will not initiate until the data review for multiple-dose Cohort M1 and single-dose

cohort S4 is complete). Each subsequent dose level may be higher, lower, or remain the same as the preceding dose level.

Additional multiple-dose cohort(s) may be added if deemed necessary by the SRG to fully characterize the safety and tolerability of CVN766. Such additional cohorts will follow the same schedule of events as for prior multiple-dose cohorts. Additional/Alternative PK timepoints may be implemented if the SRG determines this is necessary to fully characterize the PK profile of CVN766.

All AEs reported during the Treatment Period, both within and across cohorts, up to the time of discharge, will be evaluated to assess the need for the subject and/or study termination in accordance with the prespecified criteria for discontinuation/termination (Section 6.3.1).

Additionally, the SRG may decide not to escalate the dose for a particular cohort but rather administer the same or a lower dose level to the next cohort. Additional/ Alternative PK timepoints may be implemented if the SRG determines this is necessary to fully characterize the PK profile of CVN766.

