The local laboratory will perform all clinical laboratory tests. The results of laboratory tests will be returned to the investigator, who is responsible for reviewing and filing these results. All laboratory safety data will be transferred electronically to the sponsor or designee in the format requested by the sponsor. The investigator will maintain a copy of the laboratory accreditation and the reference ranges for the laboratory used.

Laboratory reports must be signed and dated by the Investigator or sub-investigator, indicating that the report has been reviewed and any abnormalities have been assessed for clinical significance. Subjects will be referred to their primary care physician for follow-up of any clinically significant findings or where the investigator or medically trained sub-investigator deems appropriate.

All CS laboratory abnormalities must be recorded as a PTE/AE in the subject’s source documents and on the appropriate eCRF. A CS laboratory abnormality that has been verified by retesting will

be followed until the abnormality returns to an acceptable level or a satisfactory explanation has been obtained.

If subjects experience ALT or AST $>3 \times$ ULN, follow-up laboratory tests at a minimum, serum alkaline phosphatase, ALT, AST, total bilirubin, GGT, and INR should be performed within a maximum of 7 days and preferably within 48 to 72 hours after the abnormality was found.

(Please refer to Section 7.5 for discontinuation criteria and Section 9.8.3 for the appropriate guidance on Reporting of Abnormal LFT in relation to ALT or AST $>3 \times$ ULN in conjunction with total bilirubin $>2 \times$ ULN).

If the ALT or AST remains elevated $>3 \times$ ULN on these 2 consecutive occasions, the investigator must contact the Medical Monitor for consideration of additional testing, close monitoring, possible discontinuation of study medication, discussion of the relevant subject details and possible alternative etiologies. The abnormality should be recorded as an AE (please refer to Section 9.8.3 Reporting of Abnormal LFT for reporting requirements).

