9.8.3 Reporting of Abnormal LFT

If a subject is noted to have ALT or AST elevated $>3 \times \text{ULN}$ on 2 consecutive occasions, the abnormality should be recorded as an AE. In addition, an LFT Increases eCRF must be completed providing additional information on relevant recent history, risk factors, clinical signs and symptoms, and results of any additional diagnostic tests performed.

If a subject is noted to have ALT or AST $>3 \times \text{ULN}$ and total bilirubin $>2 \times \text{ULN}$ for which an alternative etiology has not been identified, the event should be recorded as an SAE and reported as per Section 9.8.2. The investigator must contact the Medical Monitor for discussion of the relevant subject details and possible alternative etiologies, such as acute viral hepatitis A or B or other acute liver disease or medical history/concurrent medical conditions. Follow-up laboratory tests as described in Section 9.1.8 must also be performed. In addition, an LFT Increases eCRF must be completed and transmitted with the SAE form (as per Section 9.8.3).

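### Section 6.3.1, item 2 drops its two-subject ALT/AST hold once bilirubin rises, and item 3 does not take back every case dropped

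*Protocol*

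**What the plan says.** Section 6.3.1 lists four events, any one of which withholds further dosing until the SRG has reviewed the data.

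- **Item 1:** two or more subjects with the same kind of event that the Investigator regards as serious or Medically Significant.
- **Item 2:** two or more subjects with ALT and/or AST >5×ULN, "in the absence of a concomitant bilirubin increase (see point 3 below". It has no exception for an alternate cause.
- **Item 3:** one or more subjects with ALT and/or AST >3×ULN plus total bilirubin >2×ULN or INR >1.5, "without findings of cholestasis or other alternate etiology to explain the elevations".
- **Item 4:** two or more subjects with ALT and/or AST >3×ULN plus listed symptoms, rash or eosinophilia >5%.

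Both copies of the protocol text have the same wording here. Three other sections bear on it.

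- **Section 7.5** stops the individual subject's dosing for, among other things, ALT or AST >3×ULN "in conjunction with elevated total bilirubin" >2×ULN or INR >1.5. It has no etiology exception.
- **Section 9.8.3** covers ALT or AST >3×ULN with bilirubin >2×ULN "for which an alternative etiology has not been identified, the event should be recorded as an SAE".
- **Section 6.1.3** gives the SRG continuing oversight: "The SRG will be responsible for ongoing review of safety, tolerability, clinical laboratory results, and available PK data".

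**The concern.** A stopping rule should not relax as the laboratory picture worsens. Item 2 hands every case with raised bilirubin to item 3, but item 3 is written for a single Hy's Law subject and carries an etiology exception that item 2 lacks. It also has a numeric bilirubin threshold, whereas item 2's exclusion has none. Some pairs may therefore leave item 2 without entering item 3.

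What would be lost is the automatic hold for subjects still being dosed. In a multiple-dose cohort "6 subjects will receive a daily dose of CVN766, and 2 subjects will receive matching placebo for 7 days". If both affected subjects belong to the same cohort and are on active drug, 6 − 2 = 4 others remain on CVN766 while the matter rests on discretion. Part 2 has no sentinel dosing, and this is the first study of the compound in humans.

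**Working it through.** No power or sample-size figure is involved. The check is a truth table of items 2 to 4. Item 1 is set aside because it depends on the Investigator's classification.

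**Inputs.** Two subjects, both with ALT/AST >5×ULN and sharing the same profile:

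- bilirubin: ≤1, >1 to 2, or >2×ULN (3 bands)
- INR: ≤1.5 or >1.5 (2)
- explanation: none, cholestasis without an identified cause, or identified alternate etiology (3)
- item 4 features (symptoms, rash or eosinophilia): no or yes (2)

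Profiles: 3 × 2 × 3 × 2 = 36.

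**Rules as worded.**

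- Item 2 is met if bilirubin ≤1×ULN (no increase).
- Item 3 is met if (bilirubin >2×ULN or INR >1.5) and there is no explanation.
- Item 4 is met if item 4 features are present.

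All profiles with item 4 features are held, and so are all with bilirubin ≤1×ULN. That leaves asymptomatic profiles with raised bilirubin:

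| Bilirubin | INR | Held by item 3 | Uncovered by items 2 to 4 |
|---|---|---|---|
| >2×ULN | ≤1.5 | no explanation | cholestasis; identified cause (2) |
| >2×ULN | >1.5 | no explanation | cholestasis; identified cause (2) |
| >1 to 2×ULN | ≤1.5 | none | no explanation; cholestasis; identified cause (3) |
| >1 to 2×ULN | >1.5 | no explanation | cholestasis; identified cause (2) |

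Uncovered: 2 + 2 + 3 + 2 = 9 of 36. Situation (a), bilirubin >2×ULN, gives 4; situation (b), >1 to 2×ULN, gives 5.

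**Worked example.** Two asymptomatic subjects, ALT/AST 6×ULN, INR 1.0:

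- bilirubin 0.8×ULN, with or without an alternate cause: item 2 is met, hold
- bilirubin 1.5×ULN, with or without an alternate cause: none of items 2 to 4 is met, no mandatory hold
- bilirubin 2.5×ULN, alternate cause: none of items 2 to 4 is met, no mandatory hold
- bilirubin 2.5×ULN, no alternate cause: item 3 is met, hold

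**Dependence on the reading.**

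- If the bilirubin increase in item 2 takes item 3's >2×ULN threshold, the two lower bands merge: 2 × 2 × 3 × 2 = 24 profiles, of which only the 4 in (a) are uncovered.
- If item 2 excludes only what item 3 actually catches, 0 are uncovered.
- If the clause is deleted, item 2 is met in every profile and 0 are uncovered.

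**Individual stops under Section 7.5.** All 4 profiles in (a) stop the affected subjects. In (b), the 2 with INR >1.5 do so too. The 3 with INR ≤1.5 do not, unless ALT/AST exceeds 8×ULN or stays >5×ULN for more than 2 weeks.

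**Route through item 1.** Section 9.8.3 makes a case an SAE when bilirubin is >2×ULN and no alternative etiology is identified. Two cases of cholestasis without an identified cause could then be SAEs of the same type, so 2 of the 4 profiles in (a) arguably reach item 1. The rule does not reach the 2 with an identified cause, nor any profile in (b).

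**The case against.** The cross-reference has a sensible purpose: item 3 is stricter, needing one subject rather than two and >3× rather than >5×ULN. On that view item 2 gives up only the cases item 3 takes, and nothing is lost. This may well be the intent, but the plain wording excludes any concomitant increase and does not say so. Attaching item 3's etiology exception to the INR limb alone would close (a), but the Hy's Law label speaks against it, and under the literal item 2 it leaves the 9 − 4 = 5 profiles of (b).

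The sequence of events is a stronger argument, and it stands for (a). When the first subject's results arrive, a cause will often not be established, so item 3 holds dosing after one subject. The pair escapes only if an explanation is accepted in each before a hold operates. An identified cause also makes drug toxicity less likely. Neither argument reaches the unexplained profile in (b).

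Other safeguards stand in part. The Investigator may class the events as serious or Medically Significant whatever the cause. Section 6.1.3 adds that "All AEs reported during the Treatment Period, both within and across cohorts, up to the time of discharge, will be evaluated", although it refers that evaluation back to the criteria in Section 6.3.1. Under Section 9.1.12, when ALT or AST stays >3×ULN on two consecutive occasions, "the investigator must contact the Medical Monitor for consideration of additional testing"; the repeat may come up to 7 days later, as long as the planned dosing period. These are routes of judgement, not automatic holds.

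A reader might infer that an unexplained Hy's Law case can go without a hold, or that such pairs escape oversight altogether. The documents support neither: item 3 covers the first, and the safeguards above rule out the second.

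**Conclusion.** The point holds as a minor defect of wording. As written, the mandatory study-level hold is not monotone: raising bilirubin can remove a hold that the same ALT/AST elevations would trigger at normal bilirubin.

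Situation (a) requires only that item 2's exclusion be applied as worded. Situation (b) also requires that an increase mean any rise above ULN, which the text neither states nor rules out. Both assume no symptoms, rash or eosinophilia >5%, and no use of item 1.

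The counts (9 of 36, 4 of 24 or 0, by reading) are combinations of rules. A reader might take them as the chance of a missed hold, but the profiles are not equally likely and the protocol gives no frequencies. The figure of 4 others on active drug is likewise conditional, not expected.

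What is missing is only the automatic pause for the remaining subjects.

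**What to change.** In Section 6.3.1, item 2, delete the clause that limits it to cases without a bilirubin increase, together with its pointer to item 3. Two or more subjects with ALT and/or AST >5×ULN would then hold dosing whatever the bilirubin. Leave item 3 unchanged as the single-subject Hy's Law trigger.

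This removes the dependence on how the cross-reference is read. It takes a one-clause amendment and no new tests, since ALT, AST, bilirubin and INR are already in the laboratory panel. The downside is possibly one extra SRG pause for cases later attributed to another cause, which item 2 already accepts when bilirubin is normal.
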